8. TREATMENT OF SUBJECTS

8.1. **Description of Study Drug**

Appropriate doses of study drug will be administered to subjects within 3 days of the first day of RT and then twice weekly (every third day \pm 1 day) thereafter until 2 weeks after completion of RT.

Patients will be seen 3, 4, 5 and 6 weeks and then at 12 weeks and 12 months after the last dose of RT, but will not be treated with study drug at those times.

8.2. Concomitant Medications

Subjects will be treated on an outpatient basis. If patients require hospitalization for non-study related complications of therapy, all possible study procedures will be performed. RT and assessment of tumor burden in all subjects will be conducted as clinically appropriate, following study-specified protocols. All subjects will receive concomitant cisplatin chemotherapy (80-100 mg/m²) for treatment of cancer of the oral cavity and oropharynx.

Concomitant drugs taken by the patient during the treatment phase and through the 6-week post-RT visit should be recorded in the eCRF. In general, the generic name of the drug should be used. Drug names, especially combination preparations, should not include the dose of each component drug in the name but should be noted in the dose-Name: "Docusate/Senna" Dose "50/8.6" rather than Name: "Docusate 50 mg - Senna 8.6 mg". Components of any mouthwash prescribed should be listed- instead of "Magic Mouthwash" recorded "Mouthwash-Maalox/Lidocaine".

The following medications/therapies should *NOT* be used in enrolled patients (from baseline through 6 weeks post-RT):

- Amifostine (Ethyol®)
- Benzydamine hydrochloride
- Cetuximab (Erbitux®)
- Cevimeline hydrochloride (Evoxac[®])
- Glutamine as a prophylactic agent for mucositis
- · Devices for mucositis including GelClair, MuGard, Episil and Caphosol
- GM-CSF (e.g., Leukine[®])
- IL-11 (Neumega[®])
- 'Magic mouthwash', 'Miracle mouthwash' or other mouthwash solutions containing any of the following:

Confidential

- Chlorhexidine
- Hydrogen peroxide
- Diphenhydramine

- Tetracycline
- Palifermin (Kepivance[®]) or other keratinocyte or fibroblast growth factor
- Pilocarpine hydrochloride (Salagen[®])
- Povidone-iodine rinses
- Steroid rinses
- Sucralfate in suspension form (use of sucralfate tablets is not proscribed)
- Other biologic response modifiers except hematopoietic growth factors for the management of anemia or myelosuppression
- Low level laser therapy
- Other investigational agents for mucositis

8.3. Treatment Compliance

Patients will be treated with an IV infusion witnessed by site personnel during their daily radiation treatment clinic appointments and, therefore, compliance with study clinic visits is expected to be high while the chemoradiation treatments are continuing.

Every effort will be made by the patient and the study staff to ensure that patients can complete the assigned tasks of the trial on schedule and as per protocol prior to being consented. Every effort should be made, when medically responsible, to avoid treatment breaks or delays.

8.4. Randomization and Blinding

Patients will be randomized 1:1 to SGX942:placebo using a randomization code generated by an independent statistician. Randomization will be performed using an Interactive Web Response System (IWRS) in a double-blind fashion. Each vial of SGX942 and the identically appearing placebo vials will be supplied and labeled with a unique blinded identifying code. The IWRS will assign vial(s) of the appropriate study material to be used for each patient and each infusion using this blinded code.

Patients will be stratified at randomization by HPV status, presence of a gastrostomy tube at randomization, and study site.

[figure not shown]
Given the extremely short half life of SGX942 (minutes), it is anticipated that knowledge of whether the patient received placebo or SGX942 will rarely be needed. If, however, the PI and/or the primary care clinical team believe that this information is necessary to optimally treat an enrolled patient, the clinical data management team (DSG) should be contacted (24 hour/7 day availability) using the contact directions available in the eCRF portal. The study drug assignment for that patient will be determined and confirmation of the study drug received will be immediately sent.

Confidential

[figure not shown]

9. STUDY DRUG MATERIALS AND MANAGEMENT

9.1. Study Drug

Amendment 3: 17 September 2019

10. ASSESSMENT OF EFFICACY

10.1. Primary Efficacy Endpoint

Clinical evaluation of mucositis will be performed and graded by trained study evaluators in accordance with WHO Oral Mucositis Grading system, as detailed in Table 8 at each study drug administration visit and once a week through 6 weeks post-RT.

The duration of SOM is the primary endpoint for this clinical trial.

SOM is defined a WHO score of ≥ 3 (3 or 4). Resolution of SOM is defined as the first assessment with a WHO score ≤ 3 with no further reports of a WHO grade of ≥ 3 . The duration of SOM is defined as the number of days from the first WHO score ≥ 3 to the first day with WHO score ≤ 3 with no further occurrence of WHO score ≥ 3 . If the patient has not met the requirements for resolution of SOM by the 6-week post-RT visit, he/she will be considered censored at that visit (or point of discontinuation of the study, if the patient discontinues prior to that timepoint). To facilitate calculation of a log-rank test without censoring patients with desirable outcomes (no SOM), patients who do not experience SOM will be treated as having a duration of SOM of 0.01 days. The primary endpoint analysis will be conducted in the mITT population.

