10.2.2.3. Duration of Ulcerative Oral Mucositis (UOM)

UOM is defined as a WHO score ≥ 2 . Resolution of UOM is defined as the first assessment with a WHO score ≤ 2 with no further reports of a WHO grade of ≥ 2 . The duration of UOM is defined as the number of days from the first WHO score ≥ 2 to the first day with WHO score ≤ 2 with no further occurrence of WHO score ≥ 2 . If the patient has not met the requirements for resolution of

Original: 11 January 2017 Confidential Page 49 of 67

UOM by the 6-week post-RT visit, he/she will be considered censored at that visit (or point of discontinuation of the study, if the patient discontinues prior to that timepoint). For statistical reasons, patients who do not experience SOM will be treated as having a duration of UOM of 0.01. The analysis will be done in the mITT population.

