11.1.6 Assessment of Mortality Through the 12-month Post-RT Clinic Visit

All deaths through the 12-month follow-up visit will be collected. The number of deaths in each group will be compared using a standard chi-squared analysis. The number of deaths over time will be compared using a Kaplan-Meier survival curve and the survival curves compared using a log-rank test.

11.1.7 **Progression-free Survival**

The duration of progression free survival will be calculated from the date of randomization to the earliest date of the following:

Original: 11 January 2017

Page 53 of 67

- The patient died
- The patient had an imaging report of tumor progression (RECIST 1.1 evaluation of less than "Complete Response")
- The patient completed their 12 month follow-up assessment.

Patients lost-to-follow-up will be censored at the time of their last assessment.

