#### 9.1 ANALYSIS OF PRIMARY ENDPOINT

As detailed in Table 2, the clinical evaluation of mucositis will be performed and graded by trained study evaluators in accordance with the WHO Oral Mucositis Grading system at each study drug administration visit and for Week 3 through Week 6 post-RT.

SOM is defined as OM with WHO Grade  $\geq 3$ . The duration of SOM is defined as the number of days from the first WHO score  $\geq 3$  to the first day with a WHO score  $\leq 3$  with no further occurrence of a WHO score  $\geq 3$ . A log-rank test will be used to compare the duration of SOM of the two treatment groups.

Resolution of SOM is defined as the first assessment with a WHO score <3 with no further reports of a WHO grade of  $\ge 3$ . If the patient has not met the requirements for resolution of SOM by the 6-week post-RT visit, he/she will be considered censored at that visit (or the point of discontinuation from the study, if the patient discontinues prior to that time point). For statistical reasons, patients who do not experience SOM will be treated as having a duration of 0.01 days.

Possible scenarios for onset of SOM are displayed below in Figure 2, along with the derivation of duration of SOM.

[figure not shown]

Figure 2: Duration of SOM (Primary Analysis)

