#### 4. MISSING DATA FOR SOM DURATION CALCULATIONS

As noted above (Section 9.1), the primary analyses will examine the duration of SOM and censor the patient's data when missing. For clarity, censored visits will carry forward the last WHO score recorded for the subject through to discontinuation. For sensitivity analyses, the data will be analyzed assuming that the SOM remains at the last recorded WHO grade for the entire trial (irrespective of early study termination) and, again, assuming that the SOM was 0 throughout the trial period.

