## 5. ANALYSIS ADJUSTMENTS DUE TO IMPACT OF COVID-19 PANDEMIC

Reference is made to the FDA Guidance for Industry, "Statistical Considerations for Clinical Trials During the COVID-19 Public Health Emergency," June 2020. While many of the patients were in the treatment portion of their participation, the COVID-19 pandemic interrupted normal clinical operations with an impact on patient retention, the number and degree of protocol deviations, the ability to obtain protocol specified measurements, the ability to ship clinical specimens, and decreased the availability of clinical research personnel to perform protocol related activities. The ultimate impact of this unprecedented disruption in the clinical trial and the resulting number of dropouts, missing data, and partial data remains unclear at this time, Currently, the protocol specifies a last-value forward method of handling missing data and all patients in the mITT population are included in the analyses even if the final 4-6 weeks of experimental therapy is not delivered. To address the impact of the pandemic on this study, we will:

- Drop patients at specific sites in which the COVID-19 activities created extensive problems with documentation, data collection and/or patient enrollment and compliance;
- Terminate the trial early; and

•	Conduct sensitivity analyses on primary, secondary and safety analyses to understand the
	potential impact of the pandemic (with an assigned "start date" to the pandemic of January 1,
	2020 based on the onset of disease potentially impacting participating European sites).

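### Unresolved SOM is censored at study discontinuation or the 6-week visit instead of the last WHO examination: little harm with short gaps, real harm if examinations stop weeks earlier

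*Protocol*

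**What the plan says.** - **Primary endpoint.** For a patient still unresolved when the OM examinations end, Protocol 10.1 reads: "he/she will be considered censored at that visit (or point of discontinuation of the study, if the patient discontinues prior to that timepoint". SAP 9.1 has the same rule: "censored at that visit (or the point of discontinuation from the study".
- **Withdrawals.** Protocol 7.3 censors withdrawn patients in the efficacy analyses at withdrawal and excludes OM scoring from the assessments made afterwards.
- **Missing data.** SAP Appendix 1, item 4 first says that a patient's data are censored when missing, then adds: "For clarity, censored visits will carry forward the last WHO score recorded for the subject through to discontinuation". Item 5 describes the approach this way: "Currently, the protocol specifies a last-value forward method of handling missing data".
- **UOM duration.** Protocol 10.2.2.3 uses the same wording ("he/she will be considered censored at that visit"), and SAP 9.4.3 follows it.
- **Other endpoints.** The AUC (Protocol 10.2.1.1, SAP 9.4.1) stops at the last recorded WHO score. For progression-free survival, Protocol 11.1.7 says "Patients lost-to-follow-up will be censored at the time of their last assessment", while SAP 10.7 uses last known status.

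**The concern.** Resolution can only be recorded at an oral examination. Suppose a patient is at grade 3 at the last examination, on SOM day 10, and discontinuation is recorded 14 days later. As written, the patient is censored on day 24. For those 14 days the patient sits in the log-rank risk set with an event probability of zero, which amounts to imputing continued SOM. Valid censoring would end follow-up on day 10, when the patient was last known to be in SOM.

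The gap can arise in three ways: loss to follow-up that is declared late, discontinuation recorded after the last visit, or missed OM examinations in a patient who stays in the study. SAP Appendix 1, item 5 reports that COVID-19 impaired the collection of protocol measurements. It also keeps mITT patients in the analysis when the last 4-6 weeks of study drug were not delivered. That does not prove the examinations were missed, but WHO grading is done at the drug visits.

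At stake is the primary log-rank test. Unobserved SOM time lowers the apparent resolution rate in whichever arm has more of it.

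**Working it through.** **1. Inputs from the documents.** Median SOM duration is 13 days (placebo) v 8 days (SGX942), with 90% power, 1:1 allocation and 95 evaluable per arm (Protocol 12.4, SAP 3.1). Tests are two-sided at 5% (SAP 3.3). Examinations are twice weekly on study drug, then weekly to 6 weeks post-RT (Protocol 10.1, Table 7).

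**2. The plan's own figure.** With exponential durations the hazard ratio is 8/13 = 0.615. Freedman events = (1.960 + 1.282)² × [(1 + 0.615)/(1 − 0.615)]² = 10.51 × 4.2² ≈ 186, close to the planned 190. The sample size reproduces and is not disputed.

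**3. Chance that SOM resolves unseen in a gap of g days:** 1 − 2^(−g/median).

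| Gap (days) | Placebo | SGX942 |
|---|---|---|
| 3 | 15% | 23% |
| 7 | 31% | 46% |
| 14 | 53% | 70% |
| 28 | 78% | 91% |
| 42 | 89% | 97% |

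**4. Assumed loss.** The documents give neither a missed-examination rate nor a gap length. Assume examinations stop at a time uniform over days 0-28 after SOM onset. The average chance of still being in SOM at that time is [median/(28 ln 2)] × [1 − 2^(−28/median)]: 0.52 at a median of 13 days and 0.38 at 8 days. If 20% of each arm stop, about 10% (placebo) and 7.5% (SGX942) are lost while in SOM. With medians of 13 days in both arms, 30% v 10% stopping means about 16% v 5% lost in SOM.

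**5. Power, 95 per arm, medians 13 v 8, 20% stopping in each arm** (log-rank simulation; each cell is censoring at the last examination v as written).

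| Gap (days) | Run A (2000 trials) | Run B |
|---|---|---|
| 3 | 0.88 v 0.88 | – |
| 7 | – | 0.88 v 0.86 |
| 14 | 0.88 v 0.85 | 0.86 v 0.83 |
| 28 | 0.87 v 0.78 | 0.88 v 0.76 |
| 42 | 0.88 v 0.72 | – |

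Run A treats time as continuous. A further check that places examinations on a 3.5-day grid (1500 trials) gives 0.87 v 0.68 at 42 days. The loss is therefore about 3 points at 14 days and 16-19 points at 42 days. In run A the estimated placebo median rises from 13.1 to about 14 days for gaps of 14 days or more.

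**6. Type I error, medians 13 v 13.** With 20% stopping in each arm, the two-sided error as written is 5.0-5.4% at every gap in run A. With 30% placebo v 10% SGX942 stopping, the chance of a false SGX942 benefit (nominal 2.5%) is:

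| Gap (days) | Last examination (run A) | As written (run A) | As written (run B) |
|---|---|---|---|
| 3 | 3.0% | 4.0% | – |
| 7 | – | – | 5% |
| 14 | 2.1% | 7.8% | 10% |
| 28 | 2.4% | 16.5% | 22% |
| 42 | 2.6% | 25.6% | – |

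Run B gives about 2.5% when censoring is at the last examination. With the imbalance reversed, the inflation in run A is of similar size but counts against SGX942.

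**7. Unequal loss with a true effect (run A).** If 15% of placebo and 30% of SGX942 patients stop, power falls from about 0.88 to 0.72, 0.52 and 0.37 at 14, 28 and 42 days.

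**The case against.** The strongest reply is that the planned schedule leaves little room for harm. Patients in SOM are due for examination at least weekly, because the conditional week 5 visit is kept for anyone at grade 2 or above. Formal withdrawals should fall within days of an examination, and a patient examined at week 6 and still at grade 3 or higher is censored on an examination date. This stands: at gaps of 2-7 days the power cost is at most about 2 points.

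The rule also says censored at the visit, which presupposes that one took place. For a patient who stays in the study but has no 6-week examination, no date is given. That too is correct. It makes the rule ambiguous for exactly the patients who could have the longest gaps.

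Other analyses give some protection. Protocol 10.2.2.5 and SAP 9.2 measure duration only to the last SOM assessment, but one legible scenario in SAP Figure 3 still censors at the 6-week visit, and the status of early dropouts is not legible. The two missing-data sensitivity analyses hold the last grade for the whole trial or set it to 0. Neither is shown to censor at the last examination.

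The opening of SAP Appendix 1, item 4 could be read as censoring at the last examination, but its clarifying sentence points the other way. SAP Figure 2, which shows the derivation, is not available here.

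The contrast with progression-free survival concerns a different endpoint, so it is not a contradiction.

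**Conclusion.** The censoring date is wrong as written and should be fixed, for SOM duration and for UOM duration. The harm depends on gap length. It is nil for patients examined at week 6, small at 2-7 days, and roughly 3-20 power points at 2-6 weeks with 20% loss per arm. All these sizes rest on assumed loss rates and gaps, exponential durations and 95 patients per arm. Monte Carlo error is about 1 point.

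Three stronger readings are tempting, and the documents support none of them:

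- **That the 5% error rate fails outright.** With equal loss it stays near 5%. Inflation needs unequal loss as well as long gaps, and nothing in this double-blind plan with identical visits gives rates such as 30% v 10%.
- **That the bias favours SGX942.** The direction follows whichever arm stops examinations more often. Protocol 12.5 considers that SGX942 might reduce dropout before 55 Gy, but it gives no rates and says nothing about missed examinations.
- **That the primary analysis duplicates the carry-forward sensitivity analysis.** The primary carry-forward ends at discontinuation. The sensitivity analysis holds the grade for the whole trial.

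**What to change.** Before unblinding:

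1. In Protocol 10.1 and 10.2.2.3 and SAP 9.1 and 9.4.3, state that a patient who has not met the definition of resolution is censored at the date of the last WHO assessment on or before the 6-week post-RT visit. Align the efficacy-censoring sentence in Protocol 7.3.
2. In SAP Appendix 1, item 4, remove the carry-forward sentence from the primary analysis. Keep carry-forward only as the sensitivity analysis already listed there.

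This needs changed wording and one line of derivation code, with no new data. The downside is slightly less counted follow-up time.

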10.2. Secondary Efficacy Endpoints

10.2.1 Primary Secondary Analyses

The primary secondary endpoints are listed below in hierarchical order and will be compared in the mITT population.

10.2.1.1. Severity-weighted Duration of SOM (Area-Under the SOM-Time Curve)

The severity-weighted duration of SOM will be calculated by the AUC of the SOM versus time curve. This will be calculated by the formula for baseline (t_a) to time the last reported WHO score recorded (t_b):

$$AUC(t_b - t_a) = \sum_{i=a}^{b-1} \frac{(y_i + y_{i+1})(t_{i+1} - t_i)}{2}$$

where t_i represents the date of the i^{th} WHO assessment, and y_i represents the value of the i^{th} WHO assessment for WHO assessments for which the score is ≥ 3 .

10.2.1.2. Severity-weighted Duration of UOM (Area-Under the SOM-Time Curve)

The severity-weighted duration of UOM will be calculated by the AUC of the UOM versus time curve. This will be calculated by the formula for baseline (ta) to time the last reported WHO score recorded (tb):

$$AUC(t_b - t_a) = \sum_{i=a}^{b-1} \frac{(y_i + y_{i+1})(t_{i+1} - t_i)}{2}$$

Original: 11 January 2017

where t_i represents the date of the i^{th} WHO assessment, and y_i represents the value of the i^{th} WHO assessment for WHO assessments for which the score is ≥ 2 .

10.2.1.3. Incidence of SOM

The incidence of SOM will be calculated as the percent of patients within each treatment group who have at least one WHO score ≥3.

10.2.1.4. Quality of Life

A Quality of Life Questionnaire (QoL) will be completed by each patient at Baseline, 4 weeks and at the end of study drug treatment (2 weeks post-RT) and reviewed and entered by the site personnel into the eCRF. The EORTC QLQ-C30 (version 3) and the EORTC QLQ-H&N43 instrument will be used for these assessments. The change from Baseline in the QoL at the end of the study will be compared between treatment groups.

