Approximately 260 patients with squamous cell carcinoma of the oral cavity and oropharynx scheduled to receive a minimum total cumulative radiation dose of 55 Gy fractionated as 2.0-2.2 Gy per day and concomitant cisplatin chemotherapy given as a dose of 80-100 mg/m² (every third week) will be enrolled. Subjects will be randomized to receive either 1.5 mg/kg SGX942 or placebo given as a 4-minute IV infusion using an infusion or syringe pump. Blinded study drug will be started within 3 days after starting RT and continued twice a week (2-4 calendar days apart) through 2 weeks after completion of the RT. Efficacy will be assessed by oral examination at each treatment visit and then at the 3 through 6 weeks post-RT completion visits. OM will be evaluated using the WHO Grade system and performed by observers trained on these measurements. SOM is defined as a WHO Grade of \geq 3. The duration of SOM is defined as the first time the patient has a WHO Grade \geq 3 until the first time the patient has a WHO Grade of <3 with no subsequent readings \geq 3. Patients will be randomized (1:1; 1.5 mg/kg SGX942:placebo) using an interactive web response system (IWRS). Randomization will be stratified by site, presence of prophylactic gastrostomy feeding tube, and tumor human papillomavirus (HPV) status.

Routine clinical chemistry and hematology will be obtained at Screening/Baseline, then at 3, 6, and 9 weeks while receiving study drug, and then at the 4 and 6 week post-RT completion visit. The same type of scan initially used to stage the tumor (i.e., computed tomography [CT], magnetic resonance imaging [MRI] or positron emission tomography [PET]) will be repeated at 12 weeks and 12 months after completion of the radiation therapy and compared to the initial scan using the RECIST 1.1 criteria.

Number of Patients (planned):

260 patients (130 SGX942 treated and 130 placebo treated patients) will be enrolled.

Diagnosis and Main Criteria for Inclusion:

Inclusion Criteria

Patients must meet *all* of the following criteria in order to be eligible for enrollment:

- 1. Willing and able to understand and sign an informed consent
- 2. Males or females age greater than or equal to 18 years
- 3. Biopsy-proven squamous cell carcinoma of the oral cavity or oropharynx without distant organ metastases that has been evaluated for human papillomavirus (HPV)
- Scheduled to receive cisplatin chemotherapy of 80-100 mg/m² given every third week

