12.4. Sample Size Calculation

Sample size assessments are based on testing the hypothesis of superiority with a two-sample log rank test using the median duration of SOM, an equal allocation ratio, a 90% power $(1-\beta)$, and an α level of 0.05. In the Phase 2 clinical trial, the median duration of SOM was 30 days in the placebo group and 10 days in the 1.5 mg/kg SGX942 treatment group. Because of the variability of reported results for SOM in patient population, a conservation assumption was made that the median duration of SOM among patients receiving a minimum of 55 Gy of cumulative radiation will be 13 days in the placebo group and 8 days in the SGX942 group. Using this assumption, approximately 95 evaluable patients per arm (190 patients total) will need to complete the trial.

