## 3.3 METHODOLOGY AND CONVENTIONS

Safety and efficacy data will be summarized and presented by treatment group (SGX942 and placebo) in summary tables. Continuous variables will be presented by descriptive statistics including n, mean, standard deviation, median, minimum, and maximum. Categorical variables will be tabulated by frequency count and percentage.

Unless otherwise stated, all statistical tests will be two-sided hypothesis tests performed at the 5% level of significance for main effects, and all confidence intervals will be two-sided 95% confidence intervals. All analyses will be performed using SAS® Version 9.3 or higher.

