#### 9.4.5 Quality of Life

A Quality of Life Questionnaire will be completed by each patient at Baseline, 4 weeks and end of study drug treatment (2 weeks post-RT). The EORTC QLQ-C30 (version 3) and the EORTC QLQ-H&N43 instrument will be used for these assessments. 12 multiple-item scales (fear of progression, body image, dry mouth and sticky saliva, pain in the mouth, sexuality, problems with senses, problems with shoulder, skin problems, social eating, speech, swallowing, and problems with teeth) and 7 single-

item scales (coughing, lymphoedema, neurological problems, trismus, social contact, weight loss, and problems with wound healing) will be computed and summarized by visit, including change from baseline.

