## 9.4.8 Assessment of Pain

At each study visit, the patient's assessment of their pain over the previous 24 hours will be recorded by study personnel using a scale of 1-10. Descriptive statistics of pain assessments will be summarized by visit, including change from baseline. The Wilcoxon rank sum test will be used to compare the pain scale between treatment groups at each visit.

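### QoL and pain are both recorded at Baseline, yet no baseline-adjusted comparison is specified for either; adjusting would be at least as efficient, at almost no cost

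*Protocol*

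**What the plan says.** **QoL.** The two EORTC questionnaires are completed at Baseline, at 4 weeks and at 2 weeks post-RT (protocol 6.2.6.3 and Table 7). The contrast in protocol 10.2.1.4 is: "The change from Baseline in the QoL at the end of the study will be compared between treatment groups". No test, covariate or scale is named. Protocol 12.1 refers to the SAP for details. SAP 9.4.5 lists 12 multi-item and 7 single-item H&N43 scales, which "will be computed and summarized by visit, including change from baseline". It gives no between-group test. QoL is fourth of the five endpoints in the fixed sequence, ahead of opioid use (SAP 2.2.1 and 9.3.1).

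**Pain.** Pain history is a Baseline Day procedure (protocol 6.3.2). SAP 9.4.8 summarizes change from baseline descriptively and then says: "The Wilcoxon rank sum test will be used to compare the pain scale between treatment groups at each visit". Cumulative pain is an ungated other secondary endpoint (SAP 9.3.2).

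**General.** SAP 3.3 states that, by default, "all statistical tests will be two-sided hypothesis tests performed at the 5% level of significance for main effects". Neither document plans an ANCOVA, a mixed model or any other baseline adjustment. The continuous comparisons with a named parametric test (AUC, treatment breaks, opioids) are one-way ANOVAs.

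**The concern.** A baseline value that is collected but not used as a covariate leaves between-patient variation in the error term. A plain change score subtracts the whole baseline value, which is usually too much; a plain comparison of follow-up scores subtracts none of it. ANCOVA estimates how much to subtract. It also handles chance baseline imbalance, which randomization here does not control for these measures: the strata are site, gastrostomy tube and HPV status.

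The matter counts most for QoL. Formal testing stops at the first endpoint that misses the threshold, so avoidable noise at step 4 would lower the chance of success there and the chance that opioid use at step 5 is formally tested at all. For pain, only the precision of an ungated result is at stake.

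**Working it through.** **1. The plan's own figure.** The documents size the trial only for the primary endpoint: a "two-sample log rank test using the median duration of SOM, an equal allocation ratio, a 90% power", alpha 0.05, with medians of "13 days in the placebo group and 8 days in the SGX942 group". If durations are exponential, the hazard ratio is 8/13 = 0.615. Freedman's formula gives (1.960 + 1.282)² × [(1 + 0.615)/(1 − 0.615)]² ≈ 10.51 × 17.64, which is 186 events. Schoenfeld's gives 4 × 10.51/(ln 0.615)², which is 179. The plan says "approximately 95 evaluable patients per arm (190 patients total) will need to complete the trial", and Freedman's figure is within 3% of 190 if every evaluable patient has an event. Nothing is stated on power for QoL or pain.

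**2. Inputs for QoL and pain.** From the documents: two-sided 5% level, 1:1 allocation, 95 evaluable per arm, 130 per arm enrolled. Assumed, because the documents are silent: the baseline-to-follow-up correlation ρ, the ratio r of Baseline SD to follow-up SD, and an effect of 0.4 follow-up SDs.

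**3. QoL formulas** (follow-up variance set to 1):

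- change score: 1 + r² − 2ρr, which is 2(1 − ρ) when r = 1
- ANCOVA: 1 − ρ²
- difference: (r − ρ)², which is never negative and is zero only when ρ = r

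With r = 1, the proportional reduction is 1 − (1 + ρ)/2 = (1 − ρ)/2.

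| ρ | Reduction, r = 1 | Reduction, r = 0.7 |
|---|---|---|
| 0.3 | 1 − 0.91/1.40 = 35% | 1 − 0.91/1.07 = 15% |
| 0.5 | 1 − 0.75/1.00 = 25% | 1 − 0.75/0.79 = 5% |
| 0.7 | 1 − 0.51/0.60 = 15% | 1 − 0.51/0.51 = 0% |

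**4. Illustrative QoL power**, as Φ(0.4 × √(n/2)/√V − 1.96), where V is the variance in step 3, r = 1 and n is per arm:

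| n per arm | ρ | Change score | ANCOVA |
|---|---|---|---|
| 95 | 0.3 | 64% | 82% |
| 95 | 0.5 | 79% | 89% |
| 95 | 0.7 | 94% | 97% |
| 130 | 0.5 | 90% | 96% |

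The 130 per arm is planned enrolment ("260 patients (130 SGX942 treated and 130 placebo treated patients) will be enrolled"). The mITT set will be smaller unless the extra 10% that SAP section 2 allows makes up the losses. With r = 0.7 and ρ = 0.5, a change score with 80% power rises only to about 82% under ANCOVA.

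**5. Pain.** An unadjusted follow-up score has variance 1, against 1 − ρ² when adjusted, so the reduction is ρ²: 0% at ρ = 0, 9% at 0.3 and 25% at 0.5. This was also simulated on a 1 to 10 scale, with 95 per arm, a 0.4 SD effect before rounding and 3,000 runs per setting:

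| ρ | Wilcoxon | Rank ANCOVA |
|---|---|---|
| 0 | 76% | 76% |
| 0.2 | 75% | 77% |
| 0.3 | 75% | 78% |
| 0.5 | 75% | 84% |
| 0.7 | 76% | 93% |

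Simulated type I error was 4.7% to 5.2% for both methods.

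**The case against.** The strongest reply is that the documents define no QoL test whose power could be lost. The protocol says that change will be compared, without excluding a covariate. An ANCOVA of change on Baseline gives the same treatment estimate as an ANCOVA of the end score, so the protocol sentence is compatible with the adjusted analysis. This stands. A reader might infer that QoL is tested as a raw change score and that step 4 therefore loses some 10 points of power. The documents do not support that. An unadjusted contrast is the natural reading beside the SAP's one-way ANOVAs, but it is an inference.

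Second, step 4 has a larger gap: 19 H&N43 scales are listed, with no scoring for the QLQ-C30, no designated scale and no rule for combining scales. Until that is settled, step 4 can be neither passed nor failed, and its effect on step 5 cannot be quantified. This stands too. It does not remove the point, because a test must be written anyway and the covariate belongs in the same sentence.

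Third, the size of the gain is not fixed. Equal variances may not hold: with current mucositis excluded at entry, Baseline spread on mouth-related scales could well be narrower than at the end, and the gain then shrinks or vanishes. This stands, and is why step 3 of the working shows both cases.

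Fourth, pain is ungated and its named endpoint is cumulative, whereas the Wilcoxon test is applied visit by visit. Adjusting each visit's test would still not test the named endpoint. Baseline pain is also not mucositis pain, so ρ may be low. All of this stands and makes pain a minor part of the point.

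Last, a reader might infer bias or an inflated error rate. Neither follows: under randomization both unadjusted contrasts are valid.

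**Conclusion.** The point holds as one of efficiency, not validity. Both baselines are collected, no adjustment is planned, and in large samples the adjusted comparison is never less efficient. For QoL, the variance reduction relative to a change score is 35%, 25% and 15% at ρ of 0.3, 0.5 and 0.7 with equal variances, and 15%, 5% and 0% with a Baseline SD 0.7 times the end SD. For pain it is about ρ², and possibly near zero. Every correlation, SD ratio and effect size is an assumption, so no single power loss can be attributed to the plan. The argument about the testing sequence applies to QoL alone.

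**What to change.** In protocol 10.2.1.4 and SAP 9.4.5, state that the QoL scale designated for step 4 is compared at 2 weeks post-RT by ANCOVA with that scale's Baseline score as covariate, reporting the adjusted mean difference and 95% CI. Name the scale and the pass/fail rule in the same edit; without them the covariate does not make step 4 testable. Stating the time point also removes the mismatch between the protocol's end-of-study wording and the last QoL assessment, which is at 2 weeks post-RT. Change-score summaries can stay as description.

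As a minor addition, define the cumulative pain summary in SAP 9.4.8 and compare it by rank ANCOVA with Baseline pain as covariate.

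The cost is wording in both documents and one degree of freedom per model. No new data are needed. A rule for missing Baseline scores, such as filling in the overall Baseline mean, keeps patients from being lost.
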